### **Stage 1: Product development**

The Qlarity app is proposed to include 12 modules focused on mindfulness techniques for substance use cessation, each of which will involve 2 components: a teaching component and a practice component. During Phase I, we developed the initial 4 modules of the Qlarity app in order to examine the feasibility and usability of the app, as well as the likeability and satisfaction among our target audience. The initial 4 modules developed during Phase I are as follows: 1) Introduction to Mindfulness: Understanding its Application to Substance Use and Cessation, 2) Focusing on Current Mind and Body States: Becoming Aware of Internal States and their Connection to Substance Use, 3) Being In the Moment: Observing without Judging, and 4) Making Mindful Decisions About Substance Use. We propose to use feedback from Phase I to inform the development of the full 24-component app; (12 teaching + 12 practice components) that will include the following additional concepts aimed at reducing and eliminating substance use: 5) Understanding and Taking Charge of Your Emotions: Using Mindfulness Techniques to Manage Emotional States, 6) Identifying Personal and Contextual Triggers for Use, 7) Managing High-Stress Situations: Advanced Mindfulness Skills, 8) Mindful Decision-making and Refusal Skills, 9) Establishing a Support System, 10) Effectively Utilizing Existing Supports, 11) Planning for the Future: Maintaining Sobriety, and 12) Emergency Planning: Getting Back on Track When You Slip-up.

We will use feedback from the Phase I evaluation of the initial four modules to inform and guide the development of the full app. Feedback on usability and attractiveness will be used to modify the initial modules and to provide consistency in the development of the modules. Based on this information, we will develop prototype versions of each module using Marvel, a design and rapid prototype development tool that yields functional mockups for users to interact with before any programming takes place. During an iterative process we will refine the mockups, present them to five test users, solicit their feedback, and continue to modify and refine the mockups until we arrive at an acceptable design and feature set. We will recruit adolescent test users who report current substance use from the community for this iterative process. Next, we will finalize and create all the media assets for the app, including text and graphics, images, and narration or other audio elements; build all program screens and user controls, and determine scoring algorithms and programming logic for knowledge checks and quizzes. We will incorporate a simple user registration component to allow for tracking of app usage while also ensuring security of user-collected data.

### **Stage 2: Product evaluation**

We will conduct an evaluation of the Qlarity app with 380 high-risk adolescents who are involved in the juvenile justice system. Feasibility, usability, participant satisfaction, and intervention outcomes of substance use will be evaluated in an efficacy trial. Data on: 1) frequency and duration of app use, 2) number of modules completed, 3) changes in attitudes, emotions and behaviors, and 4) type and frequency of substance use will be examined. Participants will be compensated using gift cards to Amazon in the following increments: \$20 for each of the baseline, 4 week and 3-month assessments, and \$50 bonus for completion off all three assessments. Participants in the focus groups and usability testing will receive a \$30 gift card for their time and effort.

**Study Design:** Our evaluation of the program will be conducted with 380 adolescents ages 13- 18 who are referred from the Oregon Department of Youth Services (DYS) in Lane and Multnomah Counties, Oregon. Adolescents will be randomly and equally assigned to one of two conditions: 1) Qlarity, or 2) an active comparison condition that is standard treatment through the DHS (i.e., drug court, group therapy, and case management). All participants will be instructed to attempt to reduce substance use with a target quit date of 1 month after program initiation (day 28). Self-reported 7-day and 30-day point prevalence abstinence for all substances will be measured 1 and 3 months after treatment initiation. In addition, we will collect biochemical verification of self-reported substance use; urinary drug tests will be conducted at the baseline, 1- and 3-month follow ups and will follow the same UA drug testing protocol that we have found to be successful in our current NIH funded study with adolescents in the juvenile justice system.

**Participants:** Participants will include both male and female high risk adolescents recruited from the Department of Youth Services (DYS) in Lane and Multnomah Counties, Oregon. We have a long history of successful collaborations with the DHS and have received their support for the current proposal. Inclusion criteria will be as follows: 1) ages 13-18, 2) involvement with the juvenile justice system, 3) documented substance use, 4) English-speaking, and 5) living in the community (e.g., biological/adoptive/foster parents).

**Focus Groups and Usability Testing:** Twenty high-risk adolescents will be recruited to participate as test users in the development phase to give us initial reactions to mockup of modules, and a subgroup of 10 of these participants will be recruited to participate in preliminary usability testing of the modules. Feedback from usability testing will be used to inform adaptations to the app. The prototype app will then be evaluated in an efficacy trial with 380 additional high-risk adolescents. The primary outcomes of the evaluation-testing phase will be changes in adolescent substance use attitudes and behaviors and emotion regulation measured at three time points: baseline, 4 weeks post- baseline (end of treatment), and three months post-baseline. The proposed efficacy trial will evaluate the extent that the Qlarity app influences positive behavior change and will provide power estimates for later larger scale evaluation.

**Efficacy Trial:** Based on our power calculations, we will recruit 380 adolescents who are involved in the juvenile justice system. We have a long history of cooperation with the DHS and have well-established recruitment procedures. Eligible adolescents and their consenting parents will be recruited on a continual basis and will be included in the study for 3 months post-baseline. The participants will be randomly and equally assigned to the Qlarity condition ( $n = 190$ ) or the DC standard treatment condition ( $n = 190$ ) following adolescent assent and parent consent. Given that all youth will be involved in the juvenile justice system, we will assess all services offered and accessed by youth in both conditions.

Based on our prior experience, we expect many of the youth to be under orders to be participating in urine screening or other intervention services through DHS. Data from our current and prior studies with this population suggest that despite receiving random urine screens as part of their probationary status, 90% of youth are involved in ongoing alcohol, tobacco or other drug use (79% alcohol; 68% tobacco; 81% marijuana, and 53% other drug; 90% positive for one or more substance) at the time of referral. We will track additional services, including mandated urine screens, via official DHS reports and using a services utilization measure at each follow-up time point.

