### **Overview of the Proposed Intervention Conditions**

We propose to randomize youth into one of two conditions, outlined below.

**Qlarity.** Subjects randomized to Qlarity will be provided in-person assistance in loading the Qlarity app onto their phone immediately following their baseline interview and assessment. Once the app is loaded onto their phone, participants will generate a username and password. The proposed modules will each include a teaching and a practice component that uses mindfulness techniques to reduce or avoid substance use. Modules will be “unlocked” in ascending order as participants move through the program (i.e., module 2 will be “unlocked” after completion of module 1, etc.).

**Drug Court, Group Therapy and Case Management (DC).** The DC youth will receive the usual services provided by the DHS for youth who present with drug and alcohol use, which includes involvement in drug court, and case management services for the youth and their parents that span the duration of the youth’s probation or formal accountability contract. The drug court and case management services are provided by probation officers through the DHS. The DHS will manage each case and will make all decisions on referrals to community resources, including individual therapy, family therapy, mandated urine screens, and/or inpatient or outpatient substance use treatment that might occur in addition to the typical youth skill building groups and case management services. None of the usual services that youth in the respective study conditions receive will be affected by their participation in the study. We will track the youths’ and parents’ use of services as part of the interviews with a service utilization measure and official DHS reports of urine screens at each assessment. With these data, we will examine the type and length of treatment received for youth in both conditions, as well as the timing and outcome of urine screens over the course of the study. This services utilization measure has been used in previous work and has been useful for examining treatment impact.

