**Main-effects analyses.** Tests of the general effectiveness of the Qlarity app within this three-panel (pretest, 1- month, and 3-month follow-up) randomized trial requires an analysis that accounts for the dependence of multiple assessments nested within participants that were assigned to conditions. Thus, we will test most of our research hypotheses with random effects growth models within the hierarchical and structural equation modeling (SEM) frameworks with individual variability in change in study outcomes from pretest to 3-months nested within individuals. Following Singer and Willet when constructing the longitudinal model, we will (a) examine empirical growth plots; (b) fit an unconditional means model; (c) fit an unconditional linear growth model; (d) fit unconditional non-linear models; and (e) compare models of longitudinal change from the previous two steps using the Akaike Information Criterion. Individual variability change in the outcomes from baseline to the 3-month follow-up assessment will be modeled as a function of intervention condition. Intervention condition by time interactions will test whether groups differ on individual trajectories over the course of the study period. We will also use logistic regression models reporting odds ratios (OR) to test for differential rates of abstinence at the 3-month follow-up assessments with intervention condition a two-level predictor.

**Moderator effects.** Moderating effects of demographics (gender and minority status) and number of baseline offenses will be explored by adding the moderator to the random effects growth models described above. The multiplicative interaction term between the participant level moderators constitute a three-way cross-level interaction with time in the growth models and addresses whether the level of the baseline moderator impacted the magnitude of intervention condition on change in the outcome. All significant cross-level interactions will be probed by computing sample-estimated intercepts and slopes of the trajectories of the outcomes at conditional levels of the moderator, separately, within the Qlarity and usual care group (i.e., simple trajectories) using methods described by Curran (Curran, Bauer et al. 2006).

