**Power considerations.** The assumptions for the power estimates include a sample size of 380 participants, Type II error rate of 20% ( $\beta = .20$ ) and a 2-tailed alpha = .05. Power estimates for multilevel growth models require assumptions that are not easily established in longitudinal studies (e.g., complete data, homogeneous random-effects covariance structures within conditions). Thus we rely on the fact that power for multilevel growth models has been shown to surpass that of the mixed-model ANCOVA. The proposed growth models, then, will detect smaller differences between conditions than the ANCOVA models on which power estimates were based. Allowing for intent-to-treat analyses that makes use of all available data using missing data techniques described above and a pretest covariate  $r^2 = .25$ , there is sufficient power to detect main effects for condition of Cohen's  $d = .25$  (small effect size) and detect condition by moderator effects of  $d = .35$  (small to medium effect). The smallest subsample expected for decomposition of significant moderating effects is approximately 150 minority participants (75 per condition) which will provide sufficient power ( $>.80$ ) to detect condition effects of  $d = .40$  (medium effect). The study is also powered to detect small to medium between condition effect size differences (ORs = 2.05 – 2.25) for the logistic regression models predicting an estimated 15-20% substance use abstinence rates at follow-up. Using mediation effect size guidelines from Kenny for a model containing a dichotomous independent variable and a continuous mediator, effect sizes of .02, .15, and .40 derived from the product of  $d$  and  $r$ , represent small, medium, and large effect sizes respectively. Assuming small to moderate effects for the indirect pathway ( $r = .20$ ), the proposed sample size has sufficient power ( $>.94$ ) to detect small effect sizes or greater ( $dr = .04$ ) for tests of mediation. Process analyses involving correlation coefficients will have adequate power to detect small to medium effects ( $r = .20$ ).

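### Youth are recruited in two counties, but no stratification by county is specified and no prespecified model or moderator includes county

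*Combined protocol and SAP*

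**What the plan says.** **Sites.** Stage 2: Product evaluation (Study Design) has youth "referred from the Oregon Department of Youth Services (DYS) in Lane and Multnomah Counties, Oregon". The Participants paragraph of that section repeats the two counties. County is not mentioned anywhere else in the documents.

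**Allocation.** Study Design states "Adolescents will be randomly and equally assigned to one of two conditions". The Efficacy Trial paragraph says "The participants will be randomly and equally assigned to the Qlarity condition" and gives 190 per arm. Neither names a sequence method, blocking or a stratification factor.

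**Services.** Under Overview of the Proposed Intervention Conditions, "The drug court and case management services are provided by probation officers through the DHS", and "The DHS will manage each case and will make all decisions on referrals to community resources". The same paragraph adds: "None of the usual services that youth in the respective study conditions receive will be affected by their participation in the study".

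**Models.** Data Analysis (Main-effects analyses) states "Individual variability change in the outcomes from baseline to the 3-month follow-up assessment will be modeled as a function of intervention condition". Condition by time is the test. The 3-month abstinence logistic model has condition as its only stated predictor. The moderators are gender, minority status and the count of baseline offences. Power considerations counts one covariate, the pretest.

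**Other covariates.** The only other route into the models is under Preliminary analyses: the arms are compared at baseline on demographics and all baseline measures, and whatever differs becomes a covariate. County is not named there.

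**The concern.** County of referral is known for every youth before randomisation. Probation officers deliver the local services and the agency decides referrals case by case, so it is plausible, though not shown, that outcome levels or trends differ by county. If they do, three things follow from leaving county out:

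- The part of the county difference that the pretest or the individual intercepts do not absorb stays in the residual.
- If allocation is not stratified, a chance difference between arms in county mix feeds into the condition estimate.
- The trial does not look at whether the effect is similar in the two counties. The Focus Groups and Usability Testing paragraph says the trial is meant to supply power estimates for a larger evaluation, which makes that comparison useful.

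The baseline-difference rule is a weak substitute. It depends on a significance test, does nothing for balance at allocation, recovers no precision when the arms happen to be balanced, and leaves the model open until the data are seen.

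**Working it through.** **Inputs from the documents:** 190 per arm (Efficacy Trial); d = .25, two-sided alpha .05, 80% power and pretest r² = .25 (Power considerations).

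**Assumed, because the documents give no county figures:** county difference δ of 0.3-0.5 SD; county share f of .30 or .50 for power and .20 to .50 for imbalance; 190/190 fixed for imbalance.

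**1. The plan's own figure.** The residual variance is 1 − .25 = .75. SE = √(.75 × 2/190) = .0889. Power = Φ(.25/.0889 − 1.96) = Φ(2.814 − 1.96) = .803. The required n is 2 × (1.96 + .8416)² × .75/.25² = 188.4, so 189 per arm against 190 planned. The stated power reproduces without a county term.

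**2. Stable county difference, partly absorbed by the pretest.** With r² = .25, r = .5. A difference δ present at both pretest and follow-up leaves (1 − .5)δ after adjustment. The county variance is t = f(1 − f)(.5δ)².
- δ = .3, f = .30: t = .21 × .0225 = .0047; share of .75 = 0.6%; power .806.
- δ = .5, f = .50: t = .25 × .0625 = .0156; share of .75 = 2.1%; power .811.

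**3. A difference of the same size that remains in full after the pretest.** Now t = f(1 − f)δ², and the share is t/(.75 + t).
- δ = .3, f = .30: t = .0189; share 2.5%; power .813.
- δ = .5, f = .50: t = .0625; share 7.7%; power .834.

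Dividing t by .75 instead moves the last figure only to .836. If the plan's .75 is read as already net of county, power without the term is .771-.794 in this case and the term restores .803. The gain is then again about 1 to 3 points.

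**4. No county effect.** With t = 0, power stays at .803.

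**5. Chance imbalance without stratification.** The number of youth from one county in an arm is hypergeometric.

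| County share | SD of arm difference in share | Chance of a gap of 10 points or more |
|---|---|---|
| 20% | 4.1 points | 1.4% |
| 30% | 4.7 points | 3.3% |
| 50% | 5.1 points | 5.1% |

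A 10-point gap with a 0.3 SD county difference shifts the estimate by .10 × .3 = 0.03 SD, against a target of 0.25.

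**6. Would the baseline rule pick county up?** The plan gives no threshold. At .05, a test of county share would trigger at a gap of about 1.96 × √(f(1 − f) × 2/190), which is 8 points at f = .20 and 10 points at f = .50. In roughly 95% of allocations county would stay out.

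**7. County-by-condition.** With an even split, the SE of the difference between the two county effects is twice the main-effect SE. The smallest difference detectable with 80% power is then about 2 × .249 = .50 SD, and it is larger with an uneven split.

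**The case against.** The case against has several parts, and most of it stands.

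- **Unstratified allocation.** A reader might infer that allocation is simple and unstratified. The documents do not say so: they are silent on method. All that can be said is that no stratification is specified.
- **Two comparators.** A reader might infer two county agencies delivering two versions of usual care. The documents describe neither. Stage 2 names one state department, and the conditions section refers to the DHS.
- **Bias.** Both arms keep usual services, so a county difference in services reaches both arms and does not bias the comparison. Chance imbalance is also already reflected in the standard error.
- **Error term.** It is tempting to say that any county difference stays in the error. In the planned growth model, a stable difference in level is carried by the individual intercepts and drops out of within-person change. Only a county difference in change adds noise to the condition-by-time test. Under the ANCOVA basis used for power, the pretest absorbs about half of a stable difference. This is why step 2, not step 3, fits a stable difference.
- **Partly handled.** The baseline rule could bring county in, and service use and agency urine screens are recorded in both arms, which speaks to comparator content more directly than a county label. Neither puts county in a model in advance.
- **Logistic model.** The linear precision argument does not carry over directly to the odds ratio, and no gain is claimed for it here.

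What remains is that a site variable known for every youth is absent from every prespecified model, and that including it costs almost nothing.

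**Conclusion.** The point holds as a minor matter of efficiency and prespecification. Under the stated assumptions, power rises from .803 to about .806-.811 for a stable 0.3-0.5 SD county difference, to at most about .83 if such a difference survives the pretest, and not at all if county is unrelated to outcome. A large county imbalance is unlikely at N = 380, and its effect would be small beside the target. These sizes rest on assumed county differences and splits and on the plan's ANCOVA approximation.

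It should not be inferred that the trial is biased or that the power statement fails. The power figure reproduces, and nothing in the documents shows that the counties differ.

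**What to change.** 1. State the randomisation method. If enrolment has not started, stratify the 1:1 allocation by county, with one list per county.
2. Prespecify county as a fixed effect in every growth model, both as a main effect and by time, and as a covariate in the 3-month logistic model, regardless of observed balance. The by-time term matters because the test is on change.
3. State that the logistic odds ratio is then conditional on county.
4. Optionally, list county-by-condition among the moderators, labelled exploratory and of limited power. A difference between two counties could not by itself be attributed to services.

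If enrolment has begun, items 2 to 4 can still be fixed before analysis. The cost is a second randomisation list and one or two degrees of freedom per model, with no new data, staff or participants.

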## Data Analysis

**Preliminary analyses.** Prior to analysis, all variables will be checked for out-of-range values and inter- and intra-measure consistency; frequency distributions and plots will be examined for unusual data distributions or data points. Any necessary data transformations will be employed. Initial analyses will evaluate the baseline equivalence of conditions and examine attrition effects. Baseline equivalence will consist of chi-square and grouped t-tests analyses comparing intervention condition on demographic characteristics and all baseline measures. Results of the baseline equivalency will be a test of the effectiveness of randomization. Any group differences will be treated as covariates in subsequent main-effect, moderation, and mediation analyses. Attrition analyses will consist of chi-square and grouped t-tests comparing proportion of participants in each condition who fail to complete follow-up assessments (i.e., drop-outs vs. completers); the independent variables will include intervention condition, demographic characteristics, and baseline measures. Results of main effects concerning attrition will provide information about the external validity of the study, and interaction effects will provide information about potential confounding.

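### Entry requires documented use with no recency, so the 3-month abstinence test can count youth who were not using at baseline the same as youth who quit

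*Combined protocol and SAP*

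**What the plan says.** Stage 2, Participants, lists five inclusion criteria. The third is the only one on use, and it has no look-back window: "3) documented substance use, 4) English-speaking, and 5) living in the community". Baseline self-report and urine tests are collected, but neither is used for eligibility. Stage 1 does ask for recency, though only of the people who test the mock-ups: "We will recruit adolescent test users who report current substance use from the community for this iterative process".

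The Efficacy Trial paragraph says that in the sponsor's current and prior studies "90% of youth are involved in ongoing alcohol, tobacco or other drug use", and gives the figure again as "90% positive for one or more substance) at the time of referral".

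On the outcome, Study Design states: "Self-reported 7-day and 30-day point prevalence abstinence for all substances will be measured 1 and 3 months after treatment initiation". It also gives every participant a target quit date. Main-effects analyses uses logistic regression "to test for differential rates of abstinence at the 3-month follow-up assessments with intervention condition a two-level predictor". Neither place makes the outcome or the model conditional on baseline use. Baseline use could enter as a covariate only through the general rule in Preliminary analyses: "Any group differences will be treated as covariates in subsequent main-effect, moderation, and mediation analyses".

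Power considerations gives detectable odds ratios of 2.05–2.25 for models "predicting an estimated 15-20% substance use abstinence rates at follow-up". It does not say whether 15–20% is the control rate or the overall rate, or whether it describes all youth or current users.

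**The concern.** Point-prevalence abstinence at 3 months is a status, not a change. In a youth who was using at baseline it means quitting. In a youth who was not, it means not having relapsed. The entry criteria admit both, and the planned model scores them alike.

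The expected event is uncommon, so even a small stratum with a high abstinence rate carries much weight in the total. Two things are at stake. The abstinence rate cannot be read as a quit rate, although the trial sets a quit date and is meant to supply power estimates for a larger evaluation. And if the app affects the two groups differently, the pooled odds ratio is pulled towards the smaller effect.

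**Working it through.** **Inputs from the plan.** 190 per arm; two-sided alpha .05; abstinence 15–20%; odds ratios (OR) 2.05–2.25; 90% in use at referral.

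**Assumptions, not in the plan.** The 90% applies to enrolled youth, so f = 10% are non-users at baseline. A fraction s of these non-users is abstinent at 3 months in the control arm; s is varied from 50% to 90%.

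**1. The plan's own figure.** Two-proportion test, pooled variance, 190 per arm. If 15–20% is the overall rate, OR 2.25 at 15% means 10.0% vs 20.0%, power .78; OR 2.05 at 20% means 14.4% vs 25.6%, power .78. Both are close to the stated 80%. If 15–20% is the control rate, the ORs detectable at 80% power are 2.06 and 1.94. The plan's range fits the overall reading better but does not settle it.

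**2. Number of non-users.** 0.10 × 380 = 38, or 19 per arm.

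**3. Share of abstainers.** Share = f × s / rate.
- Lowest: 0.10 × 0.50 / 0.20 = 25% of control-arm abstainers.
- Central, s = 70%: 0.07 / 0.15 = 47%; 0.07 / 0.20 = 35%.
- Highest: 0.10 × 0.90 / 0.15 = 60%.

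Across both arms, with 15–20% as the control rate and no effect in non-users, the lowest case is 19 of 97.2 abstainers (20%) and the highest is 34.2 of 69.3 (49%). If 15–20% is instead the overall rate, the formula gives 25–60% for both arms together.

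**4. Power.** Here 15% or 20% is taken as the all-youth control rate. The control rate among users is (rate − f × s) / (1 − f). At s = 70% this is (.15 − .07)/.90 = 8.9%, or (.20 − .07)/.90 = 14.4%. Applying the OR to users gives 18.0% and 25.7% in the app arm. Non-users are then added back, either with no effect or with the same OR. Power is the Wald power of the log OR, with 190 per arm for all youth and 171 per arm for baseline users.

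Example (15%, OR 2.25, no effect in non-users): app-arm rate = .90 × .180 + .07 = 23.2%, and the all-youth OR is (.232/.768)/(.15/.85) = 1.71. The log OR is .538 with standard error .266, so power is .52. For users only, ln 2.25 = .811 with standard error .334, so power is .68.

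| Control rate, OR in users | s | All youth, no effect in non-users | All youth, same OR in non-users | Baseline users only |
|---|---|---|---|---|
| 15%, 2.25 | 50% | .66 | .79 | .76 |
| 15%, 2.25 | 70% | .52 | .64 | .68 |
| 15%, 2.25 | 90% | .37 | .42 | .57 |
| 20%, 2.05 | 50% | .70 | .81 | .77 |
| 20%, 2.05 | 70% | .62 | .72 | .73 |
| 20%, 2.05 | 90% | .53 | .57 | .68 |

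**5. Fewer non-users.** With f = 5%, s = 70% and no effect in non-users, power is .75 vs .80 (15%, OR 2.25) and .76 vs .80 (20%, OR 2.05). The control-arm shares fall to 23% and 18%. With f = 2%, the power gap is .01–.02.

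**The case against.** The strongest reply is that non-users are at risk for this endpoint, through relapse. The module list in Stage 1 includes maintaining sobriety and recovering from a slip, and the description of the Qlarity condition speaks of avoiding use as well as reducing it. This stands. A reader might infer that restriction always gains power, but that needs zero effect in non-users, which the documents do not support. With the same OR in non-users and half of them abstinent, the all-youth test is slightly better.

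The second reply concerns the 10%. It describes other studies, at referral, with no stated look-back, and it does not describe youth who also met criterion 3. This stands too: non-users can be enrolled, but the documents do not show how many will be. A reader might also infer that the plan's own figures put a third to a half of abstainers in this group. They do not, because persistence is nowhere stated.

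Two further inferences fail. Randomisation balances non-users in expectation, so the comparison is not systematically biased. And the all-youth ORs that fall below 2.05–2.25 in these scenarios do so by construction, because the plan's ORs were assigned to users alone. They do not show that the plan's power statement is wrong.

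Finally, the primary outcomes are changes in attitudes, behaviours and emotion regulation, analysed by growth models that include the baseline value. Those are less affected. None of this separates quitting from staying abstinent in the logistic analysis.

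**Conclusion.** The gap is real and confined to the 3-month abstinence analysis. No other section supplies a recency condition or limits that model to baseline users. Its size is uncertain: if 10% of enrolled youth are non-users and 50–90% of them are abstinent at 3 months, they make up about 25–60% of control-arm abstainers (about 20–50% across both arms on the control-rate reading), and less if criterion 3 selects users.

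The firm consequence is one of meaning, because the rate cannot be read as quitting. Loss of power is possible but conditional. At 70% persistence, the all-youth test has .52 and .62 against .68 and .73 if non-users do not respond, and .64 and .72 if they respond with the same OR.

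**What to change.** In the Main-effects analyses section:

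1. Pre-specify the 3-month abstinence analysis as cessation among youth using at baseline, defined as any self-reported use in the 30 days before baseline or a positive baseline urine test. Both measures are already scheduled, and the baseline interview precedes loading of the app, so the subset is not affected by the app. State that baseline status is recorded before the youth learns the assignment.
2. Also report the all-youth intent-to-treat analysis, with baseline use status as a covariate whether or not the arms differ on it.
3. In Power considerations, state which population the 15–20% rate and the ORs of 2.05–2.25 refer to, and whether 15–20% is a control or an overall rate.

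The cost is wording only. The cessation set falls by up to about 10% (380 − 38 = 342 before dropout) and does not capture relapse prevention in baseline non-users, which the all-youth analysis retains. Adding a recency window to criterion 3 for youth still to be enrolled is optional and not needed for this fix.
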